## OBJECTIVES – Main Study

### 1. Overall Objectives

**Aim 1: To test whether HIV+ smokers experience greater abstinence-induced cognitive deficits versus HIV- smokers.** *Compared to HIV- smokers, HIV+ smokers will exhibit greater deficits in verbal and working memory during abstinence (vs. smoking-as-usual).*

**Aim 2: To test whether HIV+ smokers have a lower probability of quitting following standard treatment compared to HIV- smokers.** *HIV+ smokers will have lower abstinence rates at EOT (vs. HIV- smokers).*

**Aim 3: To test whether the association between HIV status and smoking relapse is mediated by abstinence effects on cognitive deficits.** *Abstinence-induced cognitive deficits will predict relapse at EOT and will account for (mediate) differences in abstinence rates between HIV+ and HIV- smokers.*

**Exploratory Aim:** We will evaluate multiple cognitive domains (e.g., verbal memory, executive function, and response inhibition) to explore whether these domains uniquely predict relapse in HIV+ smokers. We will also explore potential moderators (e.g., nicotine metabolite ratio [a biomarker for rate of nicotine metabolism], nicotine dependence).

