**Cognitive Deficits may Underlie Smoking Persistence among HIV-Infected Individuals.** Convergent evidence suggests that the combination of cognitive deficits associated with HIV-1 infection and cognitive deficits that occur during smoking abstinence may create a dual challenge for HIV-infected smokers during a quit attempt. Specifically, the cognitive deficits observed in HIV-infected individuals may be exacerbated during early nicotine withdrawal, relative to HIV-uninfected individuals (**Aim 1**). Indeed, smokers with comorbid disorders associated with deficits in cognition, such as depression and schizophrenia, may be more likely to experience abstinence-induced cognitive deficits ([name] et al., 2014; George et al., 2002; Sacco et al., 2005). We theorize that the presence of HANDs coupled with a further decrease in cognitive function during abstinence promotes persistence of smoking. We propose that, following standard treatment, HIV-infected smokers will have more difficulty maintaining abstinence compared to HIV-smokers (**Aim 2**) and this difference will be explained (mediated) by abstinence-induced cognitive deficits (**Aim 3**). It is also possible that HIV-infected smokers experience abstinence-induced deficits in specific cognitive domains that are not observed in HIV-uninfected smokers (**Exploratory Aim**). For example, HANDs is associated with deficits in verbal memory (Devlin et al., 2012; Heaton et al., 2011), but verbal memory is not always impaired during smoking abstinence (Dawkins et al., 2007; Powell et al., 2002). Therefore, we will explore whether specific cognitive domains (e.g., verbal memory) are particularly important in explaining the relationship between HIV status and relapse, relative to other cognitive domains (e.g., executive function). The proposed study is uniquely positioned to identify a primary mechanism that may underlie smoking persistence among HIV-infected individuals with the goal of developing treatment approaches that target cognitive function.

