## 2. Statistical Analysis

### **Power Analysis and Sample Size.**

Our study is a longitudinal between-subject design that seeks to test the following hypotheses: 1) that HIV+ smokers experience larger abstinence-induced cognitive deficits than HIV- smokers (Aim 1); 2) have lower quit-rates than HIV-smokers following standard treatment (Aim 2); and 3) that the association between HIV status and relapse is mediated by abstinence-induced cognitive deficits (Aim 3). We have designed our study to achieve 80% power, testing at a global  $\alpha=0.05$  for each of the hypothesis families (Figure 1). Our sample size of 300 was determined primarily by Aim 2. Based on prior work, we expect a ~15% difference in abstinence rates between HIV+ and HIV- smokers (Ferketich et al., 2013; Humfleet et al., 2013; Matthews et al., 2013; Silagy et al., 2004). With 150 HIV+ vs. 150 HIV- smokers, we have 80% power to detect a difference of ~15 percentage points in point-prevalence abstinence (60% vs. 45%, 50% vs. 35%, 40% vs. 25%), using a z-test on log-odds with a type 1 error of 5%. For Aim 1, we will test the HIV status by abstinence condition (24-h abstinence vs. smoking-as-usual) interaction for 5 cognitive measures using a linear regression with one between- and one within-subjects factor. We will correct for 5 tests using  $\alpha=0.01$ . We have 80% power to detect medium effect sizes (Cohen's  $d=0.4$ ). For Aim 3, we will test whether abstinence-induced cognitive deficits predict quit rates and, using SEM, test whether cognitive deficits mediate the effect of HIV status on quitting. The primary aim will be to test the overall fraction of the effect mediated, which will be tested at  $\alpha=0.05$ , which gives 80% power to detect small to medium effects ( $d=0.32$ ). For our exploratory aim, the component individual deficits will be treated as secondary and tested individually as part of an exploratory analysis, also with a 5% type 1 error. To characterize cognitive deficits in HIV+ smokers, 150 subjects will give us an estimate for each measure with a 95% CI that is 0.32 standard deviations wide (Upper – Lower limits). We will estimate the within-subject correlation for these as repeated measures, with a 95% CI that is 0.32 wide (Upper – Lower) if  $r=0$ , 0.24 if  $r=0.5$ , and 0.14 if  $r=0.75$ . Power was calculated using PASS software, NCSS, Kaysville, UT.

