**Aim 3.** Assuming that we find a significant effect of HIV+ status on abstinence at EOT, we will use a correlational and regression-based path model approach for examining mediation of HIV status effects (MacKinnon et al., 2007). Candidate mediators include five cognitive performance task measures (Neurocognitive Outcomes and Table 1), and will be represented as pre-post differences, continuously distributed and treated as normal. The effects of HIV status on candidate mediators, and of mediators on outcome will be assessed using a generalized path model (Stata GSEM), with the model reporting standardized coefficients. The path model partitions the effect of group on outcome into direct (and unexplained) effects versus mediated effects. We will then test the overall mediation hypothesis using the proportion of group effect explained [87, 88, 90] and the strength of each mediating pathway as follows. We will estimate the model for HIV status predicting abstinence without mediators, to estimate the direct effect of status in the unadjusted model ( $\hat{\beta}^*$ ). We will then test whether HIV status predicts the candidate mediators, and in turn, test whether mediators predict abstinence in an adjusted group effect model, and estimate the effect of HIV status in the mediator adjusted model ( $\beta^*$ ). Finally, we will calculate the proportion of HIV status effect explained, which is calculated as  $1 - (\hat{\beta}^* / \hat{\beta}^*)$ ; the standard error for this quantity is calculated using the delta method, and the mediation hypothesis will be tested using a *z*-test. The

primary analysis tested at  $\alpha=0.05$  will be global mediation – when all candidate mediators are included in the model, a significant proportion of the HIV status effect will be explained. We will also conduct a secondary analysis using products of the coefficients along each mediating path using a delta-method based z-test.

Exploratory Aim. Using the path model described above we will quantify the proportion of variance explained by each cognitive domain (e.g., executive function, verbal memory, and response inhibition) in the relationship between HIV status and abstinence rates. Since this test is exploratory, we do not have specific hypotheses about which domain will account for more variance and these analyses will be used for hypothesis generating for future work.

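### The Objectives ask which cognitive domains predict relapse in HIV+ smokers, but the Exploratory Aim analysis estimates a between-group mediated share and no HIV+ slope is specified

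*Combined protocol and SAP*

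**What the plan says.** All places are in the combined protocol and SAP.

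- **Objectives – Main Study, Overall Objectives (Exploratory Aim).** Several domains will be evaluated "to explore whether these domains uniquely predict relapse in HIV+ smokers". This is a question about prediction within one group, and the adverb implies mutual adjustment.
- **Background – Main Study, final paragraph, tagged as the Exploratory Aim.** The interest is in whether particular domains "are particularly important in explaining the relationship between HIV status and relapse". This is a mediation question that compares the groups.
- **Data Analysis, Exploratory Aim.** "Using the path model described above we will quantify the proportion of variance explained by each cognitive domain", and the quantity concerned is located "in the relationship between HIV status and abstinence rates".
- **Data Analysis, Aim 3 (the path model being reused).** It opens "Assuming that we find a significant effect of HIV+ status on abstinence at EOT". "Candidate mediators include five cognitive performance task measures". The plan will test whether HIV status predicts the mediators, then "test whether mediators predict abstinence in an adjusted group effect model". It names no HIV-by-mediator term, multi-group model or HIV+ stratum.
- **Power Analysis and Sample Size.** For the exploratory aim, the component deficits are "tested individually as part of an exploratory analysis, also with a 5% type 1 error". No model and no restriction to HIV+ smokers is given.

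**The concern.** The two wordings of the aim are different estimands, and the analysis section serves only one of them.

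A domain's mediated share depends on two links: HIV status to the domain deficit, and the deficit to abstinence. Suppose a domain strongly predicts relapse in HIV+ smokers but its deficit is about the same size in both groups. Its first link is near zero, so its mediated share is near zero, and the planned output would rank it as unimportant. This is so even if the deficit-to-abstinence slope is the same in both groups.

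The second link does not fill the gap by itself. Estimated across both groups with adjustment for HIV status and no interaction, it is an average of two group slopes. It can dilute an association confined to HIV+ smokers, or carry one confined to HIV- smokers into a statement about HIV+ smokers.

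There is also a dependency the question does not need. Whether a deficit predicts relapse among HIV+ smokers does not require the groups to differ in quit rates. Yet the path model is set up on condition of a significant Aim 2 result, so a null Aim 2 could leave the Exploratory Aim with no specified model.

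**Working it through.** **Inputs from the document.** 150 smokers per group; planning quit rates (HIV- v HIV+) of 60/45, 50/35 and 40/25 percent (Power Analysis and Sample Size); background quit rates with the patch of 10–15% in HIV+ smokers and 30% in the general population (Background). The pair 15% v 30% is the upper HIV+ figure with the general-population figure.

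**Assumed.** The document gives no domain slopes. For illustration: OR 2.0 per SD in HIV+ and 1.0 in HIV-, one predictor at a time.

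**Step 1: the plan's own HIV+-only figure.** The CI width for a cognitive measure is 2 × 1.96/√150 = 0.320 SD, which matches the stated 0.32. It concerns the precision of the cognitive measures. The plan states no precision or power for predicting relapse within HIV+ smokers.

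**Step 2: weights.** Information on a logistic slope in one group is approximately n·p·(1−p). At 15% v 30%:
- HIV+: 150 × 0.15 × 0.85 = 19.1
- HIV-: 150 × 0.30 × 0.70 = 31.5
- HIV+ share: 19.1/50.6 = 38%

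**Step 3: pooled slope and power.** With a zero slope in HIV-, the pooled log-OR is (HIV+ share) × ln 2.0. At 15% v 30% this is 0.378 × 0.693 = 0.262, so the OR is 1.30. Power is Φ(slope × √information − 1.96):
- pooled: Φ(0.262 × √50.6 − 1.96) = 46%
- HIV+ only: Φ(0.693 × √19.1 − 1.96) = 86%

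| Quit rates HIV+ / HIV- | Information HIV+ / HIV- | HIV+ share | Pooled OR | Power, pooled | Power, HIV+ only |
|---|---|---|---|---|---|
| 15 / 30 | 19.1 / 31.5 | 38% | 1.30 | 46% | 86% |
| 25 / 40 | 28.1 / 36.0 | 44% | 1.36 | 68% | 96% |
| 35 / 50 | 34.1 / 37.5 | 48% | 1.39 | 80% | 98% |
| 45 / 60 | 37.1 / 36.0 | 51% | 1.42 | 85% | 99% |

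With OR 1.6 in HIV+ instead, the pooled OR at 15/30 is 1.19, with power of 24% pooled v 54% HIV+ only. At the planning pairs, pooled power is 38–53%.

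**Step 4: simulation in both directions.** Logistic models, 1000 runs, 150 per group, quit rates 25% v 40%, assumed HIV difference of 0.4 SD in the deficit, slopes in log-odds per SD:

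| True slope HIV+ / HIV- | Common-slope model: mean (rejections) | HIV+-only model: mean (rejections) |
|---|---|---|
| 0 / −0.7 | −0.37 (81%) | 0.00 (4%) |
| −0.7 / 0 | −0.29 (61%) | −0.72 (92%) |
| −0.35 / −0.35 | −0.36 (79%) | −0.36 (41%) |

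The first row is the more troublesome error: a domain irrelevant in HIV+ smokers is flagged in most runs. The last row shows the common slope is right, and more powerful, when slopes are equal.

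**Step 5: what an added model could detect.** At 80% power and two-sided 5%, the detectable OR in HIV+ alone is exp(2.80/√19.1) = 1.90 at a 15% quit rate, 1.70 at 25% and 1.58 at 45%. The detectable ratio of ORs for the interaction is exp(2.80 × √(1/19.1 + 1/31.5)) = 2.25 at 15/30, 2.02 at 25/40 and 1.93 at 45/60. These are single-predictor values. If correlation among domains inflated the slope variance by a factor of 1.5 (assumed), the 86% in step 3 would fall to about 70%; with a factor of 2.0, to 57%.

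**The case against.** The best defence is that the Background gives the fuller statement of this aim and words it as mediation. On that reading the HIV specificity sits in the link from HIV status to the deficits, which Aim 3 tests, and the path model answers the question. That stands. A reader might infer that the Exploratory Aim has no valid analysis, and the document does not support that. What remains is the Objectives wording, which asks about HIV+ smokers and has no analysis to match.

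Three other strong readings also fail.

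- **That the path model is the only analysis.** The power section adds individual tests at 5%. They name neither a model nor the HIV+ group, and one-at-a-time tests do not address unique prediction, so they do not close the gap. They should still be acknowledged.
- **That the pooled slope always leans towards HIV- smokers because more of them quit.** The weight is p(1−p), not the number of quitters. At 60% v 45% the HIV+ share is 51%.
- **That an association confined to HIV+ smokers would probably be missed.** At OR 2.0 that describes only the 15/30 case. At the planning pairs pooled power is 68–85%. The assumed contrast, with no association at all in HIV-, is also the extreme case.

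Equal slopes are likewise inferred: the text states no such constraint, but it specifies no interaction. Finally, the aim is exploratory and no primary conclusion depends on it. That excuses low precision. It does not make a between-group share an answer to a within-group question.

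**Conclusion.** The concern holds as a mismatch between a stated aim and its analysis. The Objectives and the Background pose different questions, and the specified analysis addresses only the Background's. Followed as written, it gives no HIV+-specific estimate of whether any domain predicts relapse. The common slope can stand in for one only under equal slopes, which the plan neither states nor tests.

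Under the assumed contrast of OR 2.0 v 1.0, the common slope shows an OR of 1.30 to 1.42, and power drops from 86–99% to 46–85% across the quit rates considered. The size rests on assumed slopes and a single-predictor approximation. The mismatch itself rests on the text alone. This is a worthwhile improvement to an exploratory analysis; Aims 1 to 3 are unaffected.

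**What to change.** 1. Reconcile the wording of the Exploratory Aim in the Objectives, the Background and the Data Analysis section, listing the two questions separately if both are wanted.
2. Keep the path model for Aim 3 and for the mediation question.
3. Add, whatever the Aim 2 result, a logistic model for end-of-treatment abstinence with the domains, HIV status and domain-by-HIV terms. Report each domain's HIV+ slope with a 95% CI, both one domain at a time and mutually adjusted, together with the interaction.
4. Specify penalised estimation if HIV+ quitters are few. At a 15% quit rate there are about 22 (150 × 0.15 = 22.5) for five HIV+ domain slopes.
5. Label the analysis hypothesis-generating. State that the detectable ratio of ORs is about 1.9 to 2.25 for a single predictor, and larger when correlated domains are fitted together.

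The cost is SAP text and one further model on data already being collected. The downside is wide intervals, most of all for the mutually adjusted HIV+ slopes. If that model is not wanted, rewording the Objectives to the mediation question would remove the inconsistency but leave the HIV+ question unanswered.

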### **Power Analysis, Sample Size and Data Analysis Rhythm Monitoring Sub-Study.**

#### Sample Size.

Our study is a longitudinal between-subject design that seeks to test the following hypotheses: 1) that HIV+ smokers have higher AF burden than HIV- smokers (Aim 1); 2) AF burden will be associated with worse cognitive function (Aim 2) and more depressive symptoms (Aim 3); and 3) that the association between AF burden and cognition and depression will be strong among HIV-infected smokers. Our sample size of 50 participants was determined primarily by Aim 1. Because we are interested in AF burden (a continuous measure) rather than a diagnosis of AF, we have 80% power to detect a medium to large effect size ( $d=0.7$ ), using a t-test with a type 1 error of 5%. For Aims 2 and 3, we have 80% power to detect a correlation of  $r=0.4$  between AF burden and cognition and depressive symptoms, with  $\alpha=0.01$  to correct for multiple outcomes. The current pilot data will be used to derive effect size estimates to support a larger clinical study.

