### **Accrual - Cardio Monitoring Sub-study**

Eligible participants enrolled in the parent study will have the opportunity to participate in the cardio monitoring sub-study. We estimate that in order to achieve a sample of 50 smokers (25 HIV+ and 25 HIV-) with usable data, we will need to enroll 60 participants into the sub-study. Recruitment for the cardio monitoring sub-study ended as of March 2020.

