#### Medical Exclusion Criteria

1. Females who self-report current pregnancy, planning a pregnancy during the study, or currently breastfeeding/lactating.
2. Current diagnosis of unstable and untreated major depression, as determined by self-report & MINI (eligible if stable for at least 30 days).
3. Current or past diagnosis of psychotic disorder, as determined by self-report or MINI.
4. History of heart disease, stroke or MI, unstable angina, or tachycardia (if stable, requires Study Physician approval).
5. Uncontrolled hypertension (SBP greater than 160 or DBP greater than 100) present at Intake.
  - a. Note: If a participant presents with blood pressure greater than 160/100 at sessions occurring on Week 3 (Pre-Quit) or at any other point during the treatment period, they will not be provided with/able to continue on TN unless the study physician grants approval.
6. Previous allergic reaction to TN.
7. History of diabetes (requires Study Physician approval)
8. History of seizures (requires Study Physician approval)
9. History of stomach ulcers (requires Study Physician approval)

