### Non-invasive Rhythm Monitoring (Sub-study only)

The device, developed by iRhythm Technologies Inc (San Francisco, CA), is a FDA-approved, compact (123 x 53 x 10.7 mm), lightweight (34 grams), and water-resistant, patch-based, lead wire-free, single-use ECG monitor that adheres to the left upper chest and provides 14 days of continuous beat-to-beat ECG data. The device has higher fidelity recordings and larger storage capabilities that can provide full disclosure ECG recordings beyond traditional 24-48 hour monitors (i.e., Holter). All rhythm monitoring devices will be purchased from iRhythm Technologies. At the end of the 2-week monitoring period, participants will return the device using a pre-labeled, prepaid mailer to the iRhythm Clinical Center (Lincolnshire, IL), which is an Independent Diagnostic Testing Facility where the data are analyzed. A digital signal-processing algorithm, which has been approved by the FDA for clinical use with oversight by Certified Cardiac Technicians, will characterize potential arrhythmias by detection of the heart rate, irregularity, and morphology.

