### Atrial Fibrillation (AF) Burden.

AF burden based on non-invasive rhythm monitoring device data collected during two different study period (weeks 0-2 and weeks 8-10). Determination of AF will be confirmed by technicians with no knowledge of the present study, and only episodes of definite AF lasting > 30 seconds will be included (Solomon et al., 2016). These findings will be reviewed by [name], who will be blinded to other clinical characteristics. We will calculate the cumulative burden of AF as the percentage of analyzable wear time spent in AF. Total analyzable wear time will be calculated from the point of activation to the point of last recorded analyzable signal. This method will provide us an opportunity to compare uniformly across participants who may have different amount of device wear time.

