#### Data Analysis.

Descriptive statistics (mean, median, standard deviation, skewness, frequency, etc) will be provided for each outcome measure from the rhythm monitoring device and for the sample characteristics (age, sex). Log-transformation will be considered for continuous outcomes with skewed distributions. Multiple comparisons will be corrected and 5% type I error will be maintained to guard against the problem of false positives due to multiple testing.

Aim 1 will use linear regression with AF burden as the primary outcome and HIV status as a between-subjects factor. Cross-sectional associations between arrhythmia burden and cognitive function (Aim 2) and depression indices (Aim 3) at baseline will be assessed using multivariable linear regression with HIV status as a between-subjects factor. All models will include relevant covariates (e.g., smoking rate, age, sex). For our exploratory aim, longitudinal associations between arrhythmia burden and cognitive and psychiatric measures will be assessed using multivariable linear regression relating a) arrhythmia at baseline and b) changes in arrhythmia burden to changes in cognitive function/psychiatric measures. We will test the HIV status by time interaction and include a dichotomous variable for smoking status at end-of-treatment (abstinent vs. relapsed).

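### The rhythm sub-study's 80% power for AF burden is 68% if the test is two-sided, and the Aim 1 analysis has no rule for participants whose burden is exactly zero

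*Combined protocol and SAP*

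**What the plan says.** The Sample Size section for the rhythm sub-study says the 50 participants were chosen mainly for Aim 1, whether HIV+ smokers have higher AF burden than HIV- smokers. It claims 80% power for d=0.7 by t-test with a 5% type 1 error, on this ground: "Because we are interested in AF burden (a continuous measure) rather than a diagnosis of AF". Sidedness is not stated. No mean, standard deviation, expected share of zeros or source for d=0.7 is given.

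The accrual section sets the group sizes: to "achieve a sample of 50 smokers (25 HIV+ and 25 HIV-) with usable data, we will need to enroll 60 participants".

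The outcome section defines the measure: "We will calculate the cumulative burden of AF as the percentage of analyzable wear time spent in AF", and "only episodes of definite AF lasting > 30 seconds will be included". Each device "provides 14 days of continuous beat-to-beat ECG data".

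The sub-study Data Analysis section plans linear regression of AF burden on HIV status, with covariates such as smoking rate, age and sex in all models. On skew it says: "Log-transformation will be considered for continuous outcomes with skewed distributions". It does not mention zeros.

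The parent study's medical exclusions include "History of heart disease, stroke or MI, unstable angina, or tachycardia", although stable cases may enter with study physician approval.

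**The concern.** The power claim rests on AF burden being continuous. By its own definition it is a mixture: a spike at exactly zero for everyone without a qualifying episode, and a positive percentage for the rest. When few values are above zero, the raw mean difference and its standard deviation depend on a handful of people, and a standardised difference of 0.7 is hard to reach. The one remedy named for skew cannot be applied to a zero without an added constant, and none is given.

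The power figure also looks too high for 25 per group before any question of zeros arises.

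What is at stake is the interpretation of sub-study Aim 1 and the pilot's stated purpose, which is to supply effect sizes for a larger study. An unstable raw mean difference is a poor input for that.

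**Working it through.** **Step 1. Reproduce the stated 80%.** Inputs: n = 25 per group (accrual section); d = 0.7, t-test, 5% type 1 error (Sample Size section).

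Noncentrality = d × √(n/2) = 0.7 × √12.5 = 2.475, with 48 degrees of freedom.

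| Test | Critical t | Exact power | Normal approximation |
|---|---|---|---|
| Two-sided 5% | 2.011 | 67.9% | Φ(2.475 − 1.960) = 69.7% |
| One-sided 5% | 1.677 | 78.7% | Φ(2.475 − 1.645) = 79.7% |

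The stated figure is recovered only one-sided. Two-sided, 80% power needs d = 0.81 at this size, or 34 per group at d = 0.7. Counting all 60 enrolled (30 per group) gives a noncentrality of 0.7 × √15 = 2.711 and 76.0% two-sided. This step assumes perfectly normal data and nothing about AF.

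**Step 2. How often could everyone be zero?** If each participant has probability p of any qualifying AF, P(all 50 are zero) = (1 − p)^50. The documents give no p, so these values are assumptions:

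- p = 2%: 0.98^50 = 36%, with 1 non-zero participant expected
- p = 4%: 0.96^50 = 13%, with 2 expected
- p = 5%: 0.95^50 = 8%, with 2.5 expected

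**Step 3. Power with a spike at zero.** Assumed model: burden is 0 without AF. With AF it is lognormal, with median 1% of wear time, log-SD 1.5 and a cap at 100%, and the same distribution in both groups. There are 25 per group, a two-sided 5% test and at least 4,000 simulated trials per setting (Monte Carlo standard error at most √(0.25/4000) = 0.8 points).

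| Any AF, HIV- v HIV+ | t-test, raw burden | t-test, log(burden + 0.01) | Mann-Whitney |
|---|---|---|---|
| 5% v 20% | about 7% | about 33% | about 36% |
| 10% v 30% | about 12% | about 38% | about 40% |
| 10% v 40% | about 23% | about 69% | about 71% |

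Lower frequencies are worse. At 5% v 15% the log and rank analyses have about 20% power and the raw t-test 2-9%, varying the log-SD from 1.0 to 2.0 and the HIV+ median between equal and doubled. The attainable effect there is d = 0.13-0.28 raw and 0.32-0.37 on log(burden + 0.01), well short of 0.7. With the HIV+ median doubled, about 80% two-sided on the log scale appears only at contrasts as wide as 5% v 35% (79-83%).

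**Step 4. Does the added constant matter?** Yes. At 5% v 15% (equal medians, log-SD 1.5), log(burden + c) has 20% power with c = 0.0001 and 9% with c = 1.

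**The case against.** The strongest reply has four parts.

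*The 80% is conditional on d=0.7, and the hypothesis is directional.* This stands in part. One-sided, the figure is essentially right. In the simulations, a log-scale d of about 0.7 (5% v 30% with any AF) gave the log t-test 68-72% two-sided and 80-83% one-sided, as normal theory predicts. So the t-test does not break down at d=0.7. The fault is that sidedness is unstated and that d=0.7 has no stated basis and is hard to reach with many zeros.

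*The log option works.* This also stands. A reader might infer that the log transform fails because log(0) is undefined. With a small constant it comes within 2-3 points of the rank test, and with a doubled HIV+ median it equals or slightly beats it (37% v 37%, 48% v 46%, 76% v 74% in the three settings tabulated). What remains is that the transform is optional and the constant is unspecified.

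*AF frequency is unknown.* A reader might infer that most of the 50 will score zero and that Aim 1 has almost no chance. The definition, the 14-day windows and the cardiac exclusion make many zeros plausible, but the documents give no frequency. The exclusion does not name AF and allows approved stable cases, and the sub-study background describes raised AF risk with HIV and with tobacco use.

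*It is a small pilot with recruitment closed in March 2020.* This is true. It limits the stakes and rules out a larger sample as the remedy, but the analysis and the power statement can still be corrected.

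**Conclusion.** The point holds in two parts of different strength.

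The power statement is firm: 68% two-sided at d=0.7 with 25 per group, and 80% only at d=0.81. The plan's figure needs a one-sided test that it does not declare.

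The gap in handling zeros is also firm, because it follows from the outcome definition and the silence of the Data Analysis section. Its size is conditional. Under assumed any-AF rates of 5-10% v 20-40% and lognormal positive burden, choosing the raw scale rather than a log or rank analysis costs roughly 26 to 48 points of power (for example 33 − 7 = 26 and 71 − 23 = 48). No analysis tried reaches 80% in those settings, so a change of test improves the sub-study without restoring the claim. The documents do not support saying that the sub-study is bound to fail.

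**What to change.** 1. State whether the Aim 1 test is one- or two-sided. If two-sided, restate power as 68% at d=0.7, or 80% at d=0.81, and give the basis for the effect size.
2. Pre-specify one Aim 1 analysis that tolerates zeros and keeps the planned covariates: regression on rank-transformed burden with a permutation p-value, or regression on log(burden + c) with c fixed before the groups are compared. A plain rank test is not enough, because it would drop the adjustment the plan requires in a non-randomised comparison.
3. Report the number and proportion with any qualifying AF in each group with exact confidence intervals. Use these, with the distribution of burden among those with AF, as the pilot's input to the larger study, rather than a raw mean difference alone.
4. Do not switch to another arrhythmia if AF proves rare, since that would make the outcome depend on the data. If another burden is wanted, such as premature ventricular contractions (already named in the sub-study background), list it in advance as a secondary outcome.

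The cost is wording in the analysis plan, with no new data. The downsides are slightly less power if burden were truly normal, and a less favourable stated power.
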